In addition, we will collect EMA data from 25 participants in each condition to obtain more granular data on the momentary relationship between varenicline use, adverse events, smoking, craving, and mood in the critical first two weeks after medication use begins. Outcomes of greatest interest are the within-person relationships between medication use (e.g., adherence), medication safety (e.g., adverse events), quit rates (self-report and biochemically validated), and factors that are associated with specific treatment outcomes.

Study sites

This study will be implemented at both Los Angeles Clinical Trials (LACT) and the Arizona State University. [name] will implement the study in Los Angeles; [name] will implement the study in Phoenix.

Human Subjects Protection. Western IRB (WIRB) will be the IRB of record for this study, and the ASU IRB will receive the WIRB approvals and maintain documentation because it is the institution that has received funding from NIH. WIRB approval is required for study implementation. WIRB will maintain records for the study, and the ASU IRB will maintain a copy.

Recruitment. We are making changes below due to the COVID-19 pandemic. The COVID-19 pandemic has resulted in a drop in the number of potential participants contacting both sites in response to recruitment advertisements. Due to the lower number of respondents, we would like to increase the geographical area from which we are recruiting. By allowing for

remote participation, we will we recruit nationally in addition to local site recruitment for inperson participation.

There will be two cohorts for this study going forward: one in-person cohort, and one remote cohort. We will recruit both cohorts via paid and free (e.g. Craigslist, Facebook, etc.) advertisements, as we have for other studies. We anticipate, based on previous studies, that we will need to recruit well over 2500 potential participants, of which 700 will be screened before 432 will ultimately be randomized. Fortunately, both sites can draw from large local populations that are demographically diverse.

Participants. We will recruit male and female smokers of any race/ethnicity who are at least 21 years of age (with no upper age limit). Our anticipated recruitment plan is: 60% male, 80% white, 10% black, 7% American Indian/Alaska Native, and 3% Hispanic. No vulnerable populations (eg incarcerated, mentally handicapped, etc) will be included; the specific inclusion/exclusion are below.

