Alternatives to Participation. Any of those who are not eligible for the study will be referred to the free smoking cessation quitline available in both states. In addition, any participants who elect to drop out of the study will also be referred to the state quitline, or could potentially obtain Chantix or another medication from their healthcare provider.

Investigational Product

Product: Varenicline (generic name, product name is Chantix™)

Doses: 0.0 mg, .5mg and 1.0 mg

Product Form: Pill

Product Administration: Oral, with water

Manufacturer: Pfizer

Varenicline and Placebo. In this study, participants will be randomly assigned in double-blind fashion to use one of two doses of varenicline (.5 mg b.i.d. or 1.0mg b.i.d.) or placebo (see study design above). Both varenicline and the placebo will look identical and be in identical packaging.

Medication Dosing. Participants assigned to the 1.0 mg b.i.d. condition, which is the current FDA-recommended dosing, will follow the recommended varenicline titrated dosing schedule as follows: days 1 through 3: 0.5mg, one daily; days 4 through 7: 0.5mg, twice daily; days 8 through end of treatment: 1mg, twice daily. Those assigned to the 0.5mg bid. condition will begin use 0.5mg once daily days 1 through 3, then will begin using 0.5 b.i.d on day 4 through the end of the study. Those assigned to the placebo condition will use pills that look identical to those that are being used in the other conditions but contain no medication. The subjects in the placebo group will also titrate during the first 7 days (1 pill days 1-3, 2 pills for the duration of the treatment period). All participants will take identical looking pills at the same time throughout the study, with the only difference being the amount of varenicline included in each pill.

Product Packaging. Medication packaging for this study will be implemented at the ASU site. Two study staff will work together to package the medications, and all packaging will be double checked and tracking forms maintained by the staff to assure quality control. Medications will be shipped by FedEx or equivalent to LACT (or directly to participants if they are participating in the study remotely), where study product will be checked and a report provided back to ASU within 24 hours indicating whether all sent medications were received.

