However, we will monitor very carefully the screening and ongoing participation of all participants. Study participants will only be allowed to participate and receive medication if the study licensed healthcare provider at each site has approved their participation after reviewing screening documents. Regular visits as well as assessments between visits will provide updates on potential adverse events, and any serious events will be assessed (including for causality) by the study physicians and reported to Western IRB and the study sponsor (National Institute on Drug Abuse/NIH) within 24 hours.

We will also identify an independent safety-monitoring panel (comprised of an MD and two additional scientists to be determined) who receive reports once a year on participant safety, protocol violations, medication use, and any other relevant topics in order to assure patient safety and study integrity. The safety-monitoring panel will assess all adverse events, and will make an independent recommendation on how study staff should address any concerns that they have raised. Their report will be maintained in the study file notebook.

E. DATA MANAGEMENT AND ANALYSIS

Data Collection, Management and Storage. All participant data will be collected and stored on the password protected iPad, and all iPads will be maintained in accordance with Good Clinical Practices and FDA regulations, e.g. in locked cabinets in locked rooms with acess restricted only to study personnel. Once each month, data will be securely sent from LA Clinical Trials to the Arizona State University, where the data will be stored for analysis. We are currently implementing a different study together, and the data transfer has worked well.

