the impact of participant characteristics on the study outcomes, we will fit multivariable logistic or Poisson regression models. The odds ratio (from logistic regression) and ratio or percent change (from Poisson regression) will be reported to quantify the association.

In addition to evaluting the primary and secondary outcomes at the end of treatment (12 week), the trend over time between the initiation of treatment and at the end of the follow up period is also of interest. We will implement generalized linear mixed model (GLMM) with random intercept to account for the clustering effect (multiple visits clustered within each participant). Independent variables will include treatment condition, visit number, and other time-varying characteristics collected post radomization. We intend to use two-level GLMMs, and will perform exploratory analysis using 3-level GLMMs (visits clustered within participants, and participants clustered within sites [CA, AZ]), as we anticipate the variability from sites would be negligible.

Analysis of the Remote Cohort. We will assess the in-person and remote cohort data via separate analyses, but because the fundamental study design in the same for both, if the outcomes of the separate analyses suggest similar outcomes, we might combine the results of both groups into a single analysis.

EMA Statistical Analysis Plan. Our approach to analyzing EMA data is based on published approaches^{32,33} using GLMMs. This class of models is useful for analyzing EMA data because they allow multiple observations per subject, multiple levels of nesting (i.e., observations within weeks within subjects), multiple subject random effects, modeling of between-subjects (BS) and within-subjects (WS) variance as a function of time-invariant covariates (e.g. treatment assignment, gender, or nicotine dependence), and extension to non-normal outcomes (i.e., dichotomous, ordinal, counts). Our primary approach will be a three-level mixed model treating observations (level 1) within days (level 2) within subjects (level 3). Additionally, we will employ a time-varying effect model (TVEM)³⁴ if we find evidence that the relative association between momentary medication adherence, side effects, craving, and smoking varies over the two weeks of observation.³⁵ We present brief examples of analyses of central interest below.

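### The exploratory three-level GLMM estimates a random site variance from only two sites; a fixed site effect would be more informative at almost no cost.

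*Combined protocol and SAP*

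**What the plan says.** The Study sites section names two centres: "This study will be implemented at both Los Angeles Clinical Trials (LACT) and the Arizona State University". In the Statistical Analysis Plan, Main study, the trend analysis is set out as follows: "We intend to use two-level GLMMs, and will perform exploratory analysis using 3-level GLMMs". The third level is "participants clustered within sites [CA, AZ"], and the reason given is "as we anticipate the variability from sites would be negligible".

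Site is named in no other model. The primary week-12 logistic model contains treatment, EMA participation and their interaction. The two-level GLMM lists treatment, visit number and time-varying characteristics, and site is not time-varying.

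On the remote cohort, the Recruitment section says "we will we recruit nationally in addition to local site recruitment", and Product Packaging has medication sent to LACT "or directly to participants if they are participating in the study remotely". The paragraph on analysis of the remote cohort plans separate analyses of the two cohorts, which may be combined if their results look similar. No section says which site, if any, a remote participant is coded to.

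**The concern.** A random effect describes a population of clusters, and its variance is learned from how much the clusters differ. Two clusters supply one contrast, and so one degree of freedom. With so little information the estimated variance often falls on the boundary at zero, whether or not the sites differ.

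The plan expects negligible site variability and names site only in this model. A reader who sees an estimate at or near zero could therefore take it as support for that expectation. At stake is how a descriptive result is read: a real difference in quit rates between Los Angeles and Arizona could go unreported because the chosen model seldom shows it.

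There is also a coding gap. If the cohorts are combined, or the three-level model is fitted to remote data, the site level has no defined value for remote participants.

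**Working it through.** **The plan's own figures.** The documents give no figure for the site variance or the three-level model. The nearest one, 110 per group for 23% vs 8% at two-sided alpha 0.025, reproduces (n = 110, power 80.3%). The planning rates 8%, 23% and 30% average (8 + 23 + 30)/3 = 20.3%, which supports 20% as a working quit rate.

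**Inputs**
- Two sites (Study sites).
- Total N = 432 (Study Design). The site split and the remote share are not given, so 432/2 = 216 per site is assumed. This places every participant at a site.
- Overall quit rate 20% (assumed, as above).
- Site SD of 0.3 or 0.5 on the log-odds scale (assumed, to show a range).
- One binary outcome per participant. The planned GLMM has repeated visits and a participant random intercept, so this is a simplification.

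**Step 1: precision of the site contrast.** The variance of the difference in log-odds is v = 2/(216 × 0.2 × 0.8) = 0.0579, so the SE is 0.241.

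**Step 2: probability that the estimated variance is zero.** The observed difference d has variance v + 2·SD². The REML estimate is zero when d² < v, and the ML estimate when d² < 2v. Hence P(zero) = P(χ² on 1 df < c·v/(v + 2·SD²)), with c = 1 for REML and c = 2 for ML.

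| True site SD | v/(v + 2·SD²) | REML | ML |
|---|---|---|---|
| 0 | 1 | 68% | 84% |
| 0.3 | 0.0579/0.2379 = 0.243 | 38% | 51% |
| 0.5 | 0.0579/0.5579 = 0.104 | 25% | 35% |

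With half as many participants per site (108, for example if many take part remotely), v = 0.1157. The figures become 47% to 62% at SD 0.3 and 34% to 46% at SD 0.5.

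**Step 3: width of the interval.** Even if the two site effects were observed without error, the 95% limits for a variance on 1 df are 1/5.02 = 0.20 times and about 1,018 times the estimate.

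**Step 4: check by simulation.** Logistic data with arm rates of 8%, 23% and 30%, N = 432 split equally over two sites, and a random site intercept were fitted by maximum likelihood with quadrature (800 runs per setting, no participant random intercept). The estimated site SD was below 0.05 in 87% of runs at true SD 0, 52% at 0.3 and 36% at 0.5. A likelihood-ratio test of zero variance rejected in 1.6%, 17.6% and 39.5% of runs. The last two agree with the ML column above.

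**Step 5: the alternative.** With site as a fixed effect under the Step 1 inputs, the 95% CI for the California-vs-Arizona odds ratio is the estimate multiplied and divided by exp(1.96 × 0.241) = 1.6.

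**The case against.** The strongest reply is that nothing hangs on this model. The two-level GLMM is chosen in advance, the three-level version is labelled exploratory, and no test or threshold is attached to the site variance. That stands. A reader might infer that the plan uses the three-level fit as a check before leaving site out; the documents do not say so.

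A reader might also infer that the site variance cannot be estimated or tested at all. That is too strong. At SD 0.5 the estimate is non-zero in 65% to 75% of trials, and the test has some power, though little. Part of that weakness comes from total N: a simulation with 20 sites and N = 420 (300 runs) gave 17% power at SD 0.3, much the same as with two sites. The SD estimate was, however, near zero less often (28% vs 52%).

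It is tempting to say that remote participants belong to neither site. The documents leave this open. The Data Safety Monitoring Plan allows participation only "if the study licensed healthcare provider at each site has approved their participation after reviewing screening documents", with no exception for remote participants, so a managing site may exist. Nor would cohort differences go unhandled by default, since the cohorts are first analysed separately.

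Finally, allocation is 1:1:1 at random, so leaving out a site term does not confound the arm comparison. The primary logistic model does not use this GLMM. Both points stand and limit the impact.

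**Conclusion.** The point holds as a low-impact improvement. With only two sites, a zero variance estimate would be common even if the sites differed moderately (25% to 51% of trials over the SDs and estimation methods considered, with 216 per site). It would therefore give little support for calling site variability negligible. The percentages rest on an assumed equal split, a 20% quit rate, one outcome per participant and illustrative site SDs. They show the order of size and do not predict this trial's result. The one-degree-of-freedom problem itself needs none of these assumptions. The primary conclusions are not threatened.

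**What to change.** In the trend analysis, replace the random site level by a fixed site effect (California vs Arizona) in the two-level GLMM, and report the estimate with its 95% CI. Preferably add the same term to the week-12 logistic model.

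State how remote participants are coded. If the cohorts are combined, use one three-level factor: Arizona in-person, California in-person, remote. In an in-person-only analysis this reduces to California vs Arizona. If each remote participant does have a managing site, the three-level factor sets that information aside, so the plan should say which coding it chooses.

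The cost is a few lines of SAP text and one or two degrees of freedom. No new data are needed.

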- Adverse Events
- Concomitant Medications
- Smoking Status and Resource Utilization Assessment (See Appendix 9) (Brief site administered questionnaires assessing smoking status, smoking cessation resources used since last study visit
- Medication Adherence, and Perceived Efficacy Assessment (see Appendix 10) (Brief site administered questionnaires assessing pills taken since last study visit, and perceived efficacy of the medication.
- Modified Cigarette Evaluation Questionnaire (mCEQ), see Appendix 11). This 15item staff or subject administered questionnaire assesses the degree to which smokers experience the reinforcing effects of smoking.

Weeks 4, 8 for the In-person Cohort

- Breath Carbon Monoxide test
- Minnesota Nicotine Withdrawal Scale
- Adverse Events
- Concomitant Medications
- Smoking Status, and Resource Utilization Assessment
- Medication adherence and Perceived Efficacy Assessment
- Assess medication use by retrieving unused medication
- Modified Cigarette Evaluation Questionnaire (mCEQ)
- Dispense additional Investigational Product

*All questionnaires at this visit will take place, as much as possible, on the phone prior to the subject attending the visit as to minimize contact in response to the COVID-19 pandemic

Week 12 for the In-person Cohort

- Body weight
- Breath Carbon Monoxide test
- Minnesota Nicotine Withdrawal Scale
- Adverse Events
- Concomitant Medications
- Smoking Status, and Resource Utilization Assessment

- Medication Adherence and Perceived Efficacy Assessment
- Assess medication use by retrieving unused medication
- Modified Cigarette Evaluation Questionnaire (mCEQ)

*All questionnaires at this visit will take place, as much as possible on the phone prior to the subject attending the visit as to minimize contact in response to the COVID-19 pandemic

Week 13 (telephone call) for the In-person Cohort

- Smoking Status, and Resource Utilization Assessment
- Adverse Events
- Minnesota Nicotine Withdrawal Scale
- Concomitant Medications including Chantix[™] or other smoking cessation aids

Week 26 for the In-person Cohort

- Telephone call
- Smoking Status and Resource Utilization Assessment
- Body weight
- Breath Carbon Monoxide test

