Sample Size. The primary analysis of this study is to compare the quit rates between groups. The sample size estimation is based on the results from Oncken et al.⁶ the quit rates at 12 weeks for 0.5, 1.0 mg b.i.d. titrated groups and control group are approximately 45%, 60% and 15%. In an OTC setting, we assume the rates would reduce by half. Therefore, 23%, 30% and 8% are used to determine the sample size. Since we are interested in comparing the two active treatment arms with the control arm, to control for the overall type I error rate, the Bonferroni adjustment is applied: for each comparison, the type I error is 0.025. With 110 participants per group, we have at least 80% power to detect a difference of 23% vs. 8% (0.5mg vs. control) by the chi-square test. Even though a smaller sample size is required to detect a difference of 30% vs. 8% (1.0mg b.i.d. vs. control), we plan to enroll equal number of participants for each arm.

For the EMA component of the study, we anticipate the primary outcomes for each treatment condition in the EMA subgroup will not be statistically different from the non-EMA sample and plan to analyze the primary outcomes based on the combined sample. However, the data collected will provide information to quantify the longitudinal within subject association. In particular, we hypothesize that the severity of side effect will increase in the first 5 days after the initiation of treatment, and expect the odds of side effect at day 5 is three times the odds at day 1. Based on our simulations (type I error 0.05, 5 time points, and intra-class correlation 0.3), with 25 participants per group, we have at least 80% power to detect an odds ratio of 3.

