Data Sharing Plan. The information that we will collect includes medically-related information that is protected and must remain confidential, so all standard methods to protect participant confidentiality will be employed, including maintaining information in password protected encrypted databases to reduce the risk of a data breach. Shared data across the two study sites will likewise be password protected and encrypted. After study completion, any outside requests for data will require a data sharing agreement that assures the following: (1) all data must be maintained in a secure fashion using appropriate technology, (2) commitment to use the data only for the research purposes requested, and (3) all shared data must either be destroyed or returned, including written assurances to that effect.

Statistical Analysis Plan

Main study. The participation flow will be reported following CONSORT guidelines. Intention to treat analysis will be applied for all statistical analyses. The data collected from the study will be summarized by the descriptive statistics for overall and by treatment condiction (1mg b.i.d., .5mg b.i.d. and placebo) and by the application of EMA (yes/no). The primary analysis will include estimating and comparing the guit rates between treatment arms. We will fit a logistic regression to model the probability of smoking cessation at 12 weeks with treatment condition, application of EMA and the interaction term of the two main effects as independent variables. If the interaction term is not significant, this implies the guit rates for the same treatment condition are similar in those with and without the utilization of EMA, and we will drop the interaction term and fit a model with main effects only. The comparison will be perfromed by the Wald test from the logistic regression with Bonferroni adjustment to account for multiple comparisons. The point estimate of guit rate and 95% confidence interval (CI) for each treatment condition will be reported. If the interaction term is significant, we will conduct the comparisons in EMA and non-EMA subgroups. A similar approach will be applied to the analysis of adherence and adverse events. These two outcome variables can be analyzed as a dichotomous (yes/no) or count variable (pill count and number of adverse events), and the logistic regression and Poisson regression will be used to evaluate whether group differences occur. In the secondary analysis, to evaluate

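### The plan does not fix whether the primary analysis pools the in-person and remote cohorts; run separately, at most one cohort can reach 80% power for 0.5 mg versus placebo

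*Combined protocol and SAP*

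**What the plan says.** All references are to the combined protocol and SAP.

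- **Section C, Recruitment.** The COVID-19 change divides enrolment: "There will be two cohorts for this study going forward: one in-person cohort, and one remote cohort". No target size is given for either cohort. One recruitment total covers both: "of which 700 will be screened before 432 will ultimately be randomized".
- **Section E, Sample Size.** One calculation is given, for an undivided sample: "With 110 participants per group, we have at least 80% power to detect a difference of 23% vs. 8" (per cent), by the chi-square test, with type I error 0.025 per active-versus-placebo comparison.
- **Section E, Main study.** The primary model is one logistic regression with treatment, EMA participation and their interaction. It has no cohort term. "The comparison will be perfromed by the Wald test from the logistic regression with Bonferroni adjustment to account for multiple comparisons". The same paragraph has a further switch: "If the interaction term is significant, we will conduct the comparisons in EMA and non-EMA subgroups".
- **Section E, Analysis of the Remote Cohort.** The default comes first: "We will assess the in-person and remote cohort data via separate analyses, but because the fundamental study design in the same for both". The option to pool comes next: "if the outcomes of the separate analyses suggest similar outcomes, we might combine the results of both groups into a single analysis".

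**The concern.** Separate analysis is stated as what will happen, and pooling as something that might. The condition for pooling is that the separate outcomes look alike, but no statistic, threshold or test defines alike. The plan does not say which of the three possible results (in-person, remote, combined) answers the primary question.

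This has two consequences. First, the primary analysis can be chosen after the results are seen. Second, if the default is followed, the sample behind the power statement no longer exists. The 0.5 mg versus placebo comparison belongs to the second primary objective and is the one used to size the trial. It would be tested twice in smaller samples, and no rule covers the case where one cohort is significant and the other is not.

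**Working it through.** **Inputs.** Quit rates of 23% (0.5 mg), 30% (1.0 mg) and 8% (placebo), with alpha 0.025 per comparison (Sample Size). Allocation is 1:1:1 in both cohorts, so 432/3 = 144 per arm. Sidedness is not stated; two-sided is assumed because it reproduces the plan's 110. No dropout is deducted, because the analysis is by intention to treat; this is the most favourable case. Cohort splits are assumptions.

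**Step 1: reproduce the stated figure.** For the chi-square test without continuity correction,

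power = Φ{ [ |p1 − p2|·√n − z·√(2p̄(1 − p̄)) ] / √(p1(1 − p1) + p2(1 − p2)) }.

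With p1 = 0.23, p2 = 0.08, p̄ = 0.155, z = 2.2414 and n = 110:

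- √(2 × 0.155 × 0.845) = 0.5118
- √(0.1771 + 0.0736) = 0.5007
- (0.15 × 10.488 − 2.2414 × 0.5118)/0.5007 = (1.573 − 1.147)/0.5007 = 0.851
- Φ(0.851) = 80.3%

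The plan's 110 per group is confirmed. With all 144 per arm the same formula gives 90.4%.

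**Step 2: can both cohorts reach 80%?** Two cohorts at 110 per arm need 220 per arm, or 660 in total, against 144 and 432 planned. One cohort reaches 80% only if it holds at least 110/144 = 76% of enrolment, which leaves at most 34 per arm in the other. The conclusion does not depend on the formula: 2 × 106 = 212 with unpooled variance, 2 × 123 = 246 with continuity correction, and 2 × 91 = 182 at two-sided 0.05 all exceed 144.

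**Step 3: power by cohort, 0.5 mg versus placebo.** The Wald column is an exact binomial enumeration of the pairwise log odds ratio test, with zero cells counted as non-significant and no EMA term.

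| Assumed split per arm | Chi-square formula | Wald |
|---|---|---|
| 72 / 72 | 59.9% / 59.9% | 56.5% / 56.5% |
| 96 / 48 | 74.0% / 41.5% | 73.4% / 31.7% |
| 110 / 34 | 80.3% / 29.3% | 80.9% / 16.4% |

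**Step 4: how often the cohorts disagree when the true effects are identical.** The probability is P1(1 − P2) + P2(1 − P1), using exact power. Exact chi-square power is up to 2.0 points above the formula.

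- Chi-square, 72/72: 2 × 0.605 × 0.395 = 48%
- Chi-square, 96/48: 0.757 × 0.571 + 0.429 × 0.243 = 54%
- Chi-square, 110/34: 0.817 × 0.687 + 0.313 × 0.183 = 62%
- Wald, same formula: 49%, 59% and 71%

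**Step 5: would equal effects look similar?** With the same true 15-point difference in both cohorts, simulation puts the observed differences more than 10 points apart in 21%, 26% and 31% of trials for the three splits. The 10-point yardstick is an illustration; the plan has none.

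**Step 6: 1.0 mg versus placebo (30% versus 8%), chi-square formula.** Power is 87.9% at 72 per arm, 70.1% at 48 and 52.9% at 34; with all 144 it is 99.6%.

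**Step 7: type I error.** Suppose any separate or pooled result could be claimed (an assumption). By the planned Wald test, familywise error is then about 5% at an 8% quit rate in all arms, and 7.7–8.7% at 15%. For the pooled test alone the figures are 3.4% and 4.3%.

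**Step 8: the alternative.** One pooled logistic Wald test adjusted for cohort has 90.3%, 91.3% and 91.4% power for 0.5 mg under the three splits (4,000 simulated trials each).

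**The case against.** The strongest reply is that this is one trial. Section C describes a single three-arm design with 432 participants, there is one sample size, and Main study gives one intention-to-treat model. The remote-cohort paragraph never calls its analyses primary, so it could be read as a loosely worded addition made because of COVID-19. That reading is possible but less literal: the paragraph commits to separate analyses and only permits pooling. The reference to a combined sample under Sample Size concerns EMA and non-EMA participants, not the cohorts.

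A second reply is that separation is prudent because the cohorts differ. In person, the week 12 check is a "Breath Carbon Monoxide test"; remotely it is urine cotinine, and only for those who report not smoking. The blood-pressure and drug-screen exclusions apply in person only, and dispensing differs. These differences stand, and they justify reporting by cohort. They do not justify leaving the primary analysis open, and the plan itself regards the two designs as fundamentally the same.

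Third, the shortfall depends on unknown splits and mainly concerns one dose. At 130/14 per arm the larger cohort would have 87.0% power for 0.5 mg (the smaller 12.1%), so naming that cohort primary could work. At an even split 1.0 mg keeps 88% in each cohort. Both points stand, but the plan names no cohort as primary. The type I error issue is minor at the planned placebo rate.

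**Conclusion.** The concern holds. As written, the choice between separate and pooled primary analysis depends on the results, has no criterion and names no primary result. At two-sided 0.025, at most one cohort can have the stated 80% power for 0.5 mg versus placebo under any split of 144 per arm. Under the assumed splits of 72/72, 96/48 and 110/34, the smaller (or equal) cohort has 60%, 41.5% and 29% by chi-square. Cohorts with identical true effects disagree on significance in 48–62% of trials by chi-square and 49–71% by Wald. Pooling keeps about 90%.

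These figures rest on the plan's own quit rates, two-sided testing, full intention-to-treat numbers and illustrative cohort sizes. The arithmetic that both cohorts cannot reach 80% does not depend on the split. The power loss is chiefly a problem for 0.5 mg; it affects 1.0 mg only when one cohort is small. This should be settled before anyone sees outcomes by arm.

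**What to change.** Replace the remote-cohort paragraph with text such as:

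> The primary analysis is one logistic regression on all randomised participants (N = 432), with treatment, cohort (in-person, remote) and EMA (yes/no) as main effects. Each active arm is compared with placebo by the Wald test at two-sided 0.025. This analysis is reported whatever the by-cohort results show. Treatment-by-cohort and treatment-by-EMA interactions, and by-cohort estimates with confidence intervals, are secondary and do not change the primary analysis.

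In Main study, delete the rule that a significant EMA interaction moves the comparison into subgroups. If it stayed, it would contradict the fixed primary analysis and could rest the result on a subgroup of 25 per arm.

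Naming one cohort as primary, or setting a numerical similarity rule in advance, would also remove the ambiguity, but with less power.

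**Cost.** SAP wording only; no extra participants. The headline estimate assumes a common odds ratio across cohorts and combines two verification methods and somewhat different eligibility, which is why the by-cohort estimates should appear beside it. The EMA-willingness criterion is listed for the in-person cohort only. If EMA enrolment proves to be largely in-person, the two interaction analyses will overlap and should be read with that in mind.
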